© Author(s) (or their employer(s)) 2018. Re-use permitted under CC BY-NC. No commercial re-use. See rights and permissions. Published by BMJ.

For numbered affiliations see end of article.

Correspondence to

[name] [name];
[contact]

ABSTRACT

Introduction Robotic-assisted surgery (RAS) has emerged as an alternative minimally invasive surgical option.

Despite its growing applicability, the frequent need for pneumoperitoneum and Trendelenburg position could significantly affect respiratory mechanics during RAS. AVATaR is an international multicenter observational study aiming to assess the incidence of postoperative pulmonary complications (PPC), to characterise current practices of mechanical ventilation (MV) and to evaluate a possible association between ventilatory parameters and PPC in patients undergoing RAS.

Methods and analysis AVATaR is an observational study of surgical patients undergoing MV for general anaesthesia for RAS. The primary outcome is the incidence

of PPC during the first five postoperative days. Secondary outcomes include practice of MV, effect of surgical positioning on MV, effect of MV on clinical outcome and intraoperative complications.

Ethics and dissemination This study was approved by the Institutional Review Board of the Hospital Israelita Albert Einstein. The study results will be published in peer-reviewed journals and disseminated at international conferences.

Trial registration number NCT02989415; Pre-results.

INTRODUCTION

Minimally invasive surgery is increasingly being used due to its association with reduced

Strengths and limitations of this study

- ▶ This will be the first study to assess the incidence of postoperative pulmonary complications and the ventilatory practice in patients undergoing general anaesthesia for robotic surgery.
- ▶ This is a multinational, multicenter, prospective, observational, rather than retrospective, study and should enhance our understanding of the incidence of postoperative pulmonary complications and the ventilatory practice in this group of patients.
- ▶ Ventilatory variables will be measured at the critical points of the surgery, to assess the impact of surgical positioning and of the pneumoperitoneum in respiratory mechanics.
- ▶ Due to the absence of standardisation on the definition of postoperative pulmonary complications, some complications will not be addressed.

surgical trauma and postoperative pain, low bleeding complication rates, shorter hospital length of stay and increased patient satisfaction.^{1 2} Robotic-assisted surgery (RAS) has emerged as an alternative minimally invasive surgical option, providing increased ergonomics, magnification of the surgical field, greater amplitude of movement and higher precision.³

Despite the growing applicability of RAS, the need of pneumoperitoneum and steep head-down (Trendelenburg) position could have a marked influence on patients respiratory mechanics. Indeed, this could lead to increased intra-abdominal pressure and cephalic elevation of the diaphragm, decreasing the compliance of the respiratory system and tidal volume, as well as increasing the plateau and peak pressure.⁴⁻⁸

Postoperative pulmonary complication (PPC) usually occur between 5 and 7 days after surgery and include the development of respiratory events, such as acute respiratory failure, acute respiratory distress syndrome (ARDS), pneumonia, prolonged or unplanned mechanical ventilation, reintubation, hypoxemia, atelectasis, bronchospasm, pleural effusion, pneumothorax and respiratory depression.⁹ Approximately, 5% of patients submitted to surgery develop at least one PPC during the follow-up, resulting in longer hospital length of stay and higher mortality rates.¹⁰ The changes in respiratory mechanics induced by the surgical positioning and by the degree of pneumoperitoneum during RAS could increase the risk of PPC in this group of patients. Nevertheless, there are currently insufficient data to guide the best ventilatory strategy during RAS, with some reports suggesting that ventilatory parameters should be adjusted to maintain normocapnia, despite the associated need for high tidal volumes.^{8 11}

The aim of the AVATaR study is to investigate the incidence of PPC, characterise current ventilatory practices and evaluate the association between ventilatory parameters and outcomes in surgical patients undergoing general anaesthesia for RAS.

METHODS

Design

This is an international multicenter prospective observational study designed in accordance with the declaration of Helsinki, registered at www.clinicaltrials.gov (trial identification number NCT02989415).

Patient and public involvement

Patients or public were not involved in the study design.

Patient eligibility

Consecutive patients undergoing mechanical ventilation for general anaesthesia for RAS will be consecutively included during a period of 1 month, to be defined by each of the participating centres. The need for informed consent is determined by the Institutional Review Board of each participating centre or country, following local regulations.

Inclusion and exclusion criteria

Patients fulfilling the following inclusion criteria are included: (1) age ≥ 18 years and (2) surgical procedures performed under general anaesthesia for RAS, including head and neck, chest, cardiac and abdominal surgeries. Patients submitted to procedures during pregnancy or outside the operation room are excluded.

Steps and data collection

Local investigators at each participating centres screen all patients submitted to mechanical ventilation during general anaesthesia for RAS during a predefined period of 1 month. PPC will be collected on day 0 (end of surgery until 11:59 pm) and on postoperative days 1, 2, 3, 4 and 5 (each day goes from 00:00 to 23:59). Data collection is finished on the day of hospital discharge or on day 5, for patients who remain hospitalised (figure 1). The start date for each participating centre is flexible and is determined together with the study coordinator.

Outcomes

The primary outcome is the incidence of PPC, defined as a collapse composite endpoint of: unplanned need for oxygen therapy (defined as supplementary oxygen used due to $\text{PaO}_2 < 60$ mm Hg or $\text{SpO}_2 < 92\%$ in room air in individuals with no prior pulmonary disease or $\text{SpO}_2 < 88\%$ in individuals with prior pulmonary disease), development of acute respiratory failure (defined as $\text{PaO}_2 < 60$ mm Hg or $\text{SpO}_2 < 92\%$, despite treatment with oxygen or need for non-invasive ventilation or unplanned continuous mechanical ventilation), development of pneumonia (defined by the presence of a new or progressive radiographic infiltrate in addition to at least two of the five clinical characteristics: fever $> 38^\circ\text{C}$, leucocytosis or leucopenia (leucocyte count $> 12.0 \times 10^9/\text{L}$ or $< 4.0 \times 10^9/\text{L}$, respectively),¹² development of ARDS (defined according to Berlin criteria)¹³ and/or development of pneumothorax (defined as the presence of air between the visceral and parietal pleura; diagnosis can be made by clinical examination and chest X-ray).¹⁴

[figure not shown]

Figure 1 Study flow chart.

Secondary outcomes include practice of ventilation, severe PPC (excluding the unplanned need for oxygen), intraoperative complications (including desaturation ($\text{SpO}_2 < 92\%$ for 3 min or more), need for unplanned recruitment manoeuvres, need for ventilatory pressure reduction, hypotension (defined as systolic blood pressure $< 90\text{ mm Hg}$ or mean arterial pressure $< 65\text{ mm Hg}$ for 3 min or more or need of vasoactive drugs for correction), need for unplanned vasoactive drugs (need for vasoactive drugs not planned before and/or continuous infusion) and/or acute new arrhythmia (atrial fibrillation, sustained ventricular tachycardia, supraventricular tachycardia and/or ventricular fibrillation)), need for unplanned mechanical ventilation after surgery (including reintubation), need for intensive care unit admission, hospital length of stay and hospital mortality.

Study organisation

The steering committee includes the principal investigator, the coordinating investigator and experts in ventilatory support in surgical patients, all of whom contributed to the design and revisions of the original study protocol. The coordinating investigator is responsible for administrative management and communication with the local investigators and provided assistance to the participating clinical sites in study management, record keeping and data management. Local investigators provided structural and scientific leadership. They guaranteed the integrity of data collection and ensure timely completion of the case report forms.

Data collection

Data collection is performed using electronic case report form in the Research Electronic Data Capture

Table 1 Characteristics of the included patients

| All patients (n=) | |
|---|---------------|
| Age, years | Mean \pm SD |
| Male sex | n/Total (%) |
| BMI, kg/m^2 | Mean \pm SD |
| ASA | Mean \pm SD |
| 1 | n/Total (%) |
| 2 | n/Total (%) |
| 3 | n/Total (%) |
| 4 | n/Total (%) |
| 5 | n/Total (%) |
| ARISCAT | Mean \pm SD |
| <26 | n/Total (%) |
| 26–44 | n/Total (%) |
| ≥ 45 | n/Total (%) |
| Functional status | |
| Independent | n/Total (%) |
| Partially dependent | n/Total (%) |
| Totally dependent | n/Total (%) |
| Comorbidities | |
| Hypertension | n/Total (%) |
| Coronary disease | n/Total (%) |
| Atrial fibrillation/flutter | n/Total (%) |
| Heart failure | n/Total (%) |
| Diabetes mellitus | n/Total (%) |
| COPD | n/Total (%) |
| Asthma | n/Total (%) |
| Smoking | n/Total (%) |
| Obstructive sleep apnoea | n/Total (%) |
| Active neoplasia | n/Total (%) |
| Liver cirrhosis | n/Total (%) |
| Anaemia ($\text{Hb} < 10\text{ g/dL}$) | n/Total (%) |
| Chronic kidney disease | n/Total (%) |
| Haematological disease | n/Total (%) |
| Use of immunosuppression | n/Total (%) |
| Complications ≤ 30 days before surgery | |
| None | n/Total (%) |
| Respiratory infection | n/Total (%) |
| Use of mechanical ventilation | n/Total (%) |
| Transfusion of blood products | n/Total (%) |
| Vital signs | |
| Respiratory rate, mpm | Mean \pm SD |
| Heart rate, bpm | Mean \pm SD |
| Mean arterial pressure, mm Hg | Mean \pm SD |
| SpO_2 , % | Mean \pm SD |
| Laboratory tests | |
| Haemoglobin, g/dL | Mean \pm SD |

Continued

Table 1 Continued

| All patients (n=) | |
|------------------------------|---------------|
| Leucocytes, $\times 10^9/L$ | Mean \pm SD |
| Creatinine, mg/dL | Mean \pm SD |
| Condition of the procedure | |
| Elective | n/Total (%) |
| Urgency | n/Total (%) |
| Emergency | n/Total (%) |
| Expected duration of surgery | |
| ≤ 2 hours | n/Total (%) |
| 2–3 hours | n/Total (%) |
| >3 hours | n/Total (%) |
| Incision | |
| Peripheral | n/Total (%) |
| Low abdomen | n/Total (%) |
| High abdomen | n/Total (%) |
| Intrathoracic | n/Total (%) |
| Other | n/Total (%) |
| Surgical procedure | |
| Prostatectomy | n/Total (%) |
| Nephrectomy | n/Total (%) |
| Hysterectomy | n/Total (%) |
| Bariatric | n/Total (%) |
| Sacrocolpopexy | n/Total (%) |
| Cholecystectomy | n/Total (%) |
| Cardiac | n/Total (%) |
| Colorectal | n/Total (%) |
| Hernia | n/Total (%) |
| Head and neck | n/Total (%) |
| Pulmonary resection | n/Total (%) |
| Cystectomy | n/Total (%) |
| Pyloroplasty | n/Total (%) |
| Pyeloplasty | n/Total (%) |
| Other | n/Total (%) |

ARISCAT, assess respiratory risk in surgical patients in Catalonia; ASA, American Society of Anesthesiology; BMI, body mass index; bpm, beats per minute; COPD, chronic obstructive pulmonary disease; Hb, haemoglobin; mpm, movements per minute; SpO₂, pulse oximetry.

(REDCap, USA) via the Internet at the Clinical Research Unit system of the Hospital Israelita Albert Einstein (the case report form is available in the online Supplementary data). The system has the following functions: patient registration, data input, data cleaning, audit trail and data export for statistical analysis. Local investigators enter the data directly into the system. Instructions for using the system are available to investigators at all times. Electronic files are archived in the Hospital Israelita Albert Einstein-based server in a secure and

Table 2 Intraoperative characteristics

| All patients (n=) | |
|---|---------------|
| Type of tracheal tube | |
| Simple endotracheal | n/Total (%) |
| Double-lumen endotracheal | n/Total (%) |
| Nasotracheal | n/Total (%) |
| Endobronchial tube | n/Total (%) |
| Endobronchial blocker | n/Total (%) |
| Type of anaesthesia | |
| Total intravenous | n/Total (%) |
| Volatile | n/Total (%) |
| Balanced | n/Total (%) |
| Use of antibiotic prophylaxis | n/Total (%) |
| Use of one-lung ventilation | n/Total (%) |
| Left lung ventilated | n/Total (%) |
| Right lung ventilated | n/Total (%) |
| Use of neuroaxial blockade | n/Total (%) |
| Epidural | n/Total (%) |
| Spinal | n/Total (%) |
| Combined | n/Total (%) |
| Use of Trendelenburg during surgery | n/Total (%) |
| Normal | n/Total (%) |
| Accentuated ($\geq 40^\circ$ of the bed) | n/Total (%) |
| Reverse | n/Total (%) |
| Surgical conversion | n/Total (%) |
| Conversion to open surgery | n/Total (%) |
| Conversion to laparoscopic | n/Total (%) |
| Use of carbondioxide insufflation | n/Total (%) |
| Abdominal | n/Total (%) |
| Thoracic | n/Total (%) |
| Mediastinum | n/Total (%) |
| Use of opioids | n/Total (%) |
| Short acting | n/Total (%) |
| Long acting | n/Total (%) |
| Both | n/Total (%) |
| Use of neuromuscular blocking agents | n/Total (%) |
| Neuromuscular blockade monitoring | n/Total (%) |
| Reversal of neuromuscular blockade | n/Total (%) |
| Residual curarisation | n/Total (%) |
| Total fluid intake, mL | Mean \pm SD |
| Crystalloids, mL | Mean \pm SD |
| Synthetic colloid, mL | Mean \pm SD |
| Albumin, mL | Mean \pm SD |
| Urine output, mL | Mean \pm SD |
| Blood loss, mL | Mean \pm SD |
| Fluid balance, mL | Mean \pm SD |
| Temperature at the end of the surgery, °C | Mean \pm SD |

Continued

Table 2 Continued

| All patients (n=) | |
|-------------------------------|-------------|
| Transfusion of blood products | n/Total (%) |
| Red blood cells | n/Total (%) |
| Fresh frozen plasma | n/Total (%) |
| Platelets | n/Total (%) |
| Cryoprecipitate | n/Total (%) |
| Duration of surgery, min | Mean±SD |
| Duration of anaesthesia, min | Mean±SD |

controlled environment to maintain confidentiality. Electronic documents are controlled with password protection according to best practices.

Data management

The goal of the clinical data management plan is to provide high-quality data by adopting standardised procedures to minimise the number of errors and missing data, and consequently, to generate an accurate database for analysis. Remote monitoring is performed to signal early aberrant patterns, issues with consistency, credibility and other anomalies, according to predefined queries created in the system. Any missing and outlier data values are individually revised and completed or corrected whenever possible.

Cleaning and locking of the database

The database will be locked as soon as all data are entered and all discrepant or missing data are resolved—or if all efforts are employed and we consider that the remaining issues cannot be fixed. At this step, the data will be reviewed before database locking. After that, the study database will be locked and exported for statistical analysis. At this stage, permission for access to the database will be removed for all investigators and the database will be archived.

Sample size

All patients submitted to ventilation during general anaesthesia for RAS will be consecutively included during the period of 1 month, in a convenience sample.

Predefined statistical analysis plan

For the primary analyses, only patients undergoing abdominal surgery will be included. Also, patients in whom the surgery was converted to open or laparoscopic will be excluded. This group of patients excluded due to these reasons will be studied in a separate report. Continuous distribution of the data will be assessed by visual inspection of histograms and D'Agostino-Pearson's normality tests. Baseline characteristics will be expressed as counts and percentages, means and SD or medians and IQR whenever appropriate. Hypothesis tests will be two-sided with a significance level of 5%. We will not adjust p values for multiple comparisons. Analyses will

be performed using the R (R Core Team, 2016, Vienna, Austria) programme.

Baseline characteristics

Patients baseline characteristics will be presented as shown in mock [table 1](#).

Intraoperative characteristics

Intraoperative characteristics will be presented as shown in mock [table 2](#).

Ventilatory variables

Ventilatory variables and other interventions will be reported hourly for 6 hours and in four specific periods: (1) 5 min after induction and beginning of ventilation (T_1); (2) 5 min after CO_2 insufflation (T_2); (3) 5 min after definitive positioning (immediately before beginning surgery) (T_3) and (4) 5 min after removal of pneumoperitoneum and return to supine (T_4). Peak, plateau and driving pressure (defined as plateau minus positive-end expiratory pressure (PEEP)) and PEEP levels, tidal volume size, respiratory rate, fraction of inspired oxygen (FiO_2), static and dynamic respiratory system compliance, pulse oximetry (SpO_2), heart rate, mean arterial pressure and pressure of CO_2 insufflation over the four specific periods will be analysed using a mixed model with repeated measures and plotted in an interaction plot (mock [table 3](#)).

Primary outcome

The number of patients developing a PPC will be reported in absolute numbers and percentages (mock [table 4](#)). The impact of ventilatory variables on the development of PPC will be assessed using a generalised linear mixed-effect model. Relevant covariates included in the final multivariable model will be identified as those with $p<0.2$ in the univariable model (including centre as a random effect), clinical relevance and no statistical association with other relevant variables. In the final model, time of measurement will be included as a fixed effect together with the variables of interest and the centres and patients will be included as random effect. The linearity of each continuous predictor with the log odds outcome will be checked graphically and, if not present, a log-transformation will be performed. Pearson correlation coefficients will be used to assess collinearity between predictors. Since a high collinearity between peak, plateau and driving pressure is expected, the main model will consider the variable with the higher amount of measurements between peak or plateau pressure. Driving pressure will be considered in a sensitivity analysis, excluding PEEP, peak and plateau pressure. Finally, the intraclass correlation coefficient (ICC) will be assessed. The ICC represents the ratio of between-site variance to total variance, ranging from 0 to 1.

Secondary outcomes

Secondary outcomes will be reported as shown in mock [table 4](#).

Table 3 Intraoperative ventilation in four specific periods

| | Five minutes after induction and beginning of ventilation | | Five minutes after CO_2 insufflation | | Five minutes after definitive positioning | | Five minutes after desinsufflation and return to supine | |
|--|---|----------|---|----------|---|----------|---|----------|
| | Patients | P values | Patients | P values | Patients | P values | Patients | P values |
| Surgical positioning | | | | | | | | |
| Dorsal decubitus | n/Total (%) | | n/Total (%) | | n/Total (%) | | n/Total (%) | |
| Ventral decubitus | n/Total (%) | | n/Total (%) | | n/Total (%) | | n/Total (%) | |
| Lateral decubitus | n/Total (%) | | n/Total (%) | | n/Total (%) | | n/Total (%) | |
| Lithotomy | n/Total (%) | | n/Total (%) | | n/Total (%) | | n/Total (%) | |
| Trendelenburg | n/Total (%) | | n/Total (%) | | n/Total (%) | | n/Total (%) | |
| Reverse Trendelenburg | n/Total (%) | | n/Total (%) | | n/Total (%) | | n/Total (%) | |
| Sitting | n/Total (%) | | n/Total (%) | | n/Total (%) | | n/Total (%) | |
| Mode of ventilation | | | | | | | | |
| Pressure controlled | n/Total (%) | | n/Total (%) | | n/Total (%) | | n/Total (%) | |
| Volume controlled | n/Total (%) | | n/Total (%) | | n/Total (%) | | n/Total (%) | |
| PCVG | n/Total (%) | | n/Total (%) | | n/Total (%) | | n/Total (%) | |
| Other | n/Total (%) | | n/Total (%) | | n/Total (%) | | n/Total (%) | |
| Peak pressure, cmH_2O | Mean \pm SD | | Mean \pm SD | | Mean \pm SD | | Mean \pm SD | |
| Plateau pressure, cmH_2O | Mean \pm SD | | Mean \pm SD | | Mean \pm SD | | Mean \pm SD | |
| Driving pressure, cmH_2O | Mean \pm SD | | Mean \pm SD | | Mean \pm SD | | Mean \pm SD | |
| PEEP, cmH_2O | Mean \pm SD | | Mean \pm SD | | Mean \pm SD | | Mean \pm SD | |
| Tidal volume, mL/kg PBW | Mean \pm SD | | Mean \pm SD | | Mean \pm SD | | Mean \pm SD | |
| Respiratory rate, mpm | Mean \pm SD | | Mean \pm SD | | Mean \pm SD | | Mean \pm SD | |
| FiO_2 , % | Mean \pm SD | | Mean \pm SD | | Mean \pm SD | | Mean \pm SD | |
| Static C_{RS} , mL/ cmH_2O | Mean \pm SD | | Mean \pm SD | | Mean \pm SD | | Mean \pm SD | |
| Dynamic C_{RS} , mL/ cmH_2O | Mean \pm SD | | Mean \pm SD | | Mean \pm SD | | Mean \pm SD | |
| Use of recruitment manoeuvres | | | | | | | | |
| Increase in PEEP | n/Total (%) | | n/Total (%) | | n/Total (%) | | n/Total (%) | |
| Increase in tidal volume | n/Total (%) | | n/Total (%) | | n/Total (%) | | n/Total (%) | |
| Increase in tidal volume and PEEP | n/Total (%) | | n/Total (%) | | n/Total (%) | | n/Total (%) | |
| Manual insufflation with bag | n/Total (%) | | n/Total (%) | | n/Total (%) | | n/Total (%) | |
| CPAP | n/Total (%) | | n/Total (%) | | n/Total (%) | | n/Total (%) | |
| SpO_2 , % | Mean \pm SD | | Mean \pm SD | | Mean \pm SD | | Mean \pm SD | |
| etCO_2 , mm Hg | Mean \pm SD | | Mean \pm SD | | Mean \pm SD | | Mean \pm SD | |
| Mean arterial pressure, mm Hg | Mean \pm SD | | Mean \pm SD | | Mean \pm SD | | Mean \pm SD | |
| Heart rate, bpm | Mean \pm SD | | Mean \pm SD | | Mean \pm SD | | Mean \pm SD | |
| Pressure of CO_2 insufflation, mm Hg | Mean \pm SD | | Mean \pm SD | | Mean \pm SD | | Mean \pm SD | |

bpm, beats per minute; CPAP, continuous positive airway pressure; C_{RS} , respiratory system compliance; etCO_2 , end-tidal carbon dioxide; FiO_2 , fraction of inspired oxygen; mpm, movements per minute; PBW, predicted body weight; PCVG, pressure controlled volume guaranteed; PEEP, positive-end expiratory pressure; SpO_2 , pulse oximetry.

ETHICS AND DISSEMINATION

The study will be performed according to the national and international guidelines. The study will not begin at the participating centres until approval has been obtained

from the local Institutional Review Board for each participating centre or country, according to local regulation. Prospective written informed consent will be requested

Table 4 Clinical outcomes

| | All patients (n=) |
|--|-------------------|
| Primary outcomes | |
| Postoperative pulmonary complications | n/Total (%) |
| Unplanned need of oxygen | n/Total (%) |
| Acute respiratory failure | n/Total (%) |
| Pneumonia | n/Total (%) |
| ARDS | n/Total (%) |
| Pneumothorax | n/Total (%) |
| Secondary outcomes | |
| Severe postoperative pulmonary complications | n/Total (%) |
| Intraoperative complications | n/Total (%) |
| Desaturation | n/Total (%) |
| Unplanned recruitment manoeuvres | n/Total (%) |
| Need for ventilatory pressure reduction | n/Total (%) |
| Hypotension | n/Total (%) |
| Need for unplanned vasoactive drug | n/Total (%) |
| Acute new arrhythmia | n/Total (%) |
| Unplanned ventilation after surgery | n/Total (%) |
| Reintubation | n/Total (%) |
| New use of mechanical ventilation | n/Total (%) |
| Admission to intensive care unit | n/Total (%) |
| Hospital length of stay | Mean±SD |
| Median (IQR) | Median (IQR) |
| Hospital mortality | n/Total (%) |

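### Data collection stops at discharge or day 5, but hospital length of stay and hospital mortality are reported with no day-5 limit and no rule for patients still in hospital

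*SAP*

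**What the plan says.** Under Steps and data collection, PPC are recorded on day 0 and on postoperative days 1 to 5. The next sentence sets a general end point: "Data collection is finished on the day of hospital discharge or on day 5, for patients who remain hospitalised".

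The secondary outcomes in the Outcomes section end with "need for intensive care unit admission, hospital length of stay and hospital mortality". None of these carries a time limit.

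The Secondary outcomes paragraph of the analysis plan adds only this: "Secondary outcomes will be reported as shown in mock" Table 4. That table has a row for "Hospital length of stay", summarised as mean with SD and as median with IQR, and a row for "Hospital mortality", summarised as n/Total (%). Neither row mentions day 5.

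Two further statements bear on completeness. Data management says: "Any missing and outlier data values are individually revised and completed or corrected whenever possible". Cleaning and locking says: "The database will be locked as soon as all data are entered and all discrepant or missing data are resolved", or once every effort has been made and what remains cannot be fixed.

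**The concern.** A hospital stay ends at discharge or death, so its length and outcome are known only then. For a patient in hospital at the end of day 5, the stop rule closes collection before either is known. The text shown does not extend follow-up, censor stay at day 5, restrict mortality to day 5, or say how such patients are counted.

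If centres apply the rule as worded, the mean and SD of stay come out too low, and in-hospital deaths after day 5 are missed under a label that promises all of them. If centres read it differently, the pooled figures mix two definitions.

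The loss would not be random. The Introduction places PPC typically 5 to 7 days after surgery and links them to longer stay and higher mortality. The patients who matter most for these two outcomes are thus the likeliest to be in hospital when collection stops.

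**Working it through.** **Comparing the text.**

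| Item | Where | Time limit |
|---|---|---|
| Daily PPC record | Steps and data collection | Days 0 to 5 |
| Data collection in general | Steps and data collection, next sentence | Discharge, or day 5 if still in hospital |
| Hospital length of stay | Outcomes; Table 4 | None |
| Hospital mortality | Outcomes; Table 4 | None |

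The PPC window is already fixed in its own sentence, and the stop rule has data collection as its subject. Read literally, the second row cuts off the third and fourth for anyone who stays past day 5.

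**Illustrating the size.** The SAP gives no distribution of stay and no cap, so there is no figure of its own to reproduce. All inputs below are assumptions except the 5% in the low case.

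*Low case.* The Introduction gives about 5% of surgical patients with at least one PPC. Suppose only that share stays beyond day 5, for L days, and that the others average 3 days with SD 1. The 5% is a PPC rate and is borrowed here as a share of long stayers.

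- True mean = 0.95 × 3 + 0.05 × L. Capped mean = 0.95 × 3 + 0.05 × 5 = 3.10.
- SD = √(0.95 × (1 + 9) + 0.05 × L² − mean²). The capped SD, with L = 5, is 1.07.

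| L (days) | True mean | Capped mean lower by | True SD |
|---|---|---|---|
| 7 | 3.20 | 3.1% | 1.31 |
| 10 | 3.35 | 7.5% | 1.81 |
| 15 | 3.60 | 13.9% | 2.79 |

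*Lognormal stay*, median m, log-SD s, cap c = 5. Let a = (ln c − ln m)/s.

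- Share beyond day 5: p = 1 − Φ(a)
- True mean: m·exp(s²/2)
- Part of the mean from stays up to c: E₁ = m·exp(s²/2)·Φ(a − s)
- Capped mean: E₁ + c·p
- Mean if longer stayers are left out: E₁/(1 − p)
- Median if they are left out: m·exp(s·Φ⁻¹(0.5(1 − p)))
- Capped SD: from the analogous second moment

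Middle scenario (m = 3, s = 0.8): a = ln(5/3)/0.8 = 0.639, so p = 0.262. The true mean is 3·exp(0.32) = 4.13. E₁ = 4.13 × Φ(−0.161) = 4.13 × 0.436 = 1.80. The capped mean is 1.80 + 5 × 0.262 = 3.11, and the left-out mean is 1.80/0.738 = 2.44.

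| m, s | Beyond day 5 | Mean: true / capped / left out | SD: true / capped | Median: true / left out |
|---|---|---|---|---|
| 2, 0.6 | 6.3% | 2.39 / 2.29 / 2.10 | 1.58 / 1.23 | 2.00 / 1.91 |
| 3, 0.8 | 26.2% | 4.13 / 3.11 / 2.44 | 3.91 / 1.52 | 3.00 / 2.30 |
| 4, 1.0 | 41.2% | 6.59 / 3.50 / 2.45 | 8.64 / 1.58 | 4.00 / 2.33 |

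Over all nine combinations (m = 2, 3, 4; s = 0.6, 0.8, 1.0):

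- 6% to 41% stay beyond day 5.
- Capping lowers the mean by 4.5% to 47% and the SD by 22% to 82%. It leaves the median unchanged in all nine, because fewer than half stay longer.
- In five of the nine, more than a quarter stay longer, so the upper quartile is lost even with a cap.
- Leaving longer stayers out lowers the mean by 12% to 63% and the median by 5% to 42%.

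*Sensitivity to the cap.* Day 5 runs to 23:59, so time since surgery can approach 6 days. With c = 6, the middle scenario has 19% beyond the cap and a mean 19.3% too low (24.8% at c = 5). The smallest understatement falls from 4.5% to 2.5%. The direction does not change.

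**The case against.** The best counter-argument is that a consistent reading exists. The stop sentence directly follows the daily PPC schedule and shares its day-5 end, so it may close only those daily assessments. Outcomes named as hospital stay and hospital mortality run to discharge by their names. The sentence points to Figure 1, which is not shown, and the case report form is in an online supplement. Either may already record discharge date and vital status. If so, the data-cleaning and database-lock rules would fill any blanks, and nothing is lost.

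This stands as a limit on the claim: loss of data cannot be asserted. It does not remove the conflict. The sentence speaks of data collection in general, and a local investigator can reasonably stop at day 5. The cleaning rules help only if the fields exist and stay open after that day.

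The objection is also right that the scenario figures rest on chosen parameters, that neither capping nor omission is in the plan, that the 5% is not a rate of long stay, and that the plan does not say whether stay counts from admission or from surgery. The figures show direction and plausible scale only.

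Finally, both outcomes are descriptive, in a single column for all patients. The only outcome model specified is for PPC. That limits the weight of the point.

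**Conclusion.** The concern holds as a fault of wording with real consequences if followed. The stop rule does not cover two listed secondary outcomes, and nothing in the text shown reconciles them. Whether data would actually be lost depends on Figure 1 and the case report form.

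If the rule is applied literally and longer stays are capped, the mean stay is too low by about 3% to 14% in the low case and by 4.5% to 47% across the lognormal scenarios. The median holds as long as fewer than half stay beyond day 5 and those patients are kept as staying more than 5 days; it does not hold if they are left out. Deaths after day 5 cannot be sized from the document. The scenarios are not fitted to the abdominal, non-converted cases to which the primary analyses are restricted, and that restriction may shift the distribution.

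The PPC outcome and its model are unaffected. This should be corrected, but it does not threaten the main result.

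**What to change.** In Steps and data collection, limit the day-5 stop to the daily PPC form, and state that discharge date and vital status at hospital discharge are recorded for every patient. If the case report form already holds both, say so.

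If follow-up to discharge is not possible, rename the outcomes in the Outcomes section and Table 4 as mortality to day 5 and length of stay censored at day 5. Keep patients beyond day 5 in the denominator, report the median with the percentage who stayed longer, and drop the mean and SD of stay.

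The first option costs at most two chart-based fields per patient, with database lock waiting for the last discharge, or a single clarifying sentence if the fields exist. The second costs only relabelling. Neither needs an extra visit or procedure.
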